9.4.2 Secondary outcomes

The secondary outcome will be the proportion of study participants with end-of-year PDC \geq 80%.

In secondary analyses, the study team will compare arms against each other and adjust for any imbalanced baseline characteristics.

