3 STUDY DESIGN

Type/design of trial: randomized controlled trial

Primary objective (hypothesis): Messages using dynamic social norms, messenger effects, and processing fluency in combination will more effectively increase average end-of-year adherence level compared to usual care (no messages).

Secondary objective: To identify baseline clinical and demographic characteristics to predict the efficacy of each message.

Study population: Individuals 65 to 79 years of age taking any class of medication for hypertension, with adherence level between 60% and 85%.

Study arms (7,143 individuals each):

1. A scorecard from Humana reporting patients' medication adherence using a "refill score"
2. The Arm 1 scorecard plus dynamic social norms messaging (noting the proportion of Humana members improving their medication refill scores)
3. The Arm 1 scorecard, coming from the trusted messenger of a Humana-identified pharmacist taking the same medication.
4. A modified scorecard increasing processing fluency through a visual metaphor of "closing the ring"
5. The Arm 4 scorecard plus dynamic social norms messaging
6. The Arm 4 scorecard, coming from the trusted messenger of a Humana-identified pharmacist taking the same medication.
7. No mailed message (usual care)

Study location: Humana

Duration of enrollment period: Individuals will be enrolled at a single time point at study launch

Duration of follow-up period: Approximately 6 months

Description of intervention and administration: Study participants will be randomized into receiving one of 6 mailed messages (arms 1-6 above) informing them of their medication refill score, or no message. Two messages will be sent during the intervention: The first message will contain the baseline refill score. The second message will note any changes in the refill score.

Description of descriptive and outcome variables from the medical, insurance, and pharmaceutical records:

Medical variables: None

Insurance / enrollment variables:

- Patient enrollment in a Medicare Advantage Prescription Drug plan insured by Humana in plan year 2023
- Patient age in plan year 2023
- Patient Gender
- Patient Race

Pharmaceutical variables:

- Current adherence on hypertension medications (PDC) as of July 2023
- Unique prescription fills for hypertension medication use
- Unique prescription fills for other medications
- End-of-year adherence on hypertension medications (PDC) in 2023 (following intervention)

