6.2.2 Enrollment, Baseline, and/or Randomization

Enrollment

59,997 randomly selected study participants will be enrolled from the pool of Humana members who meet all study inclusion criteria and none of the study exclusion criteria.

Baseline Assessments

- Current adherence level as of July 2023.
- Historical, and demographic patient characteristics including age, gender, race, clinical comorbidities and other medication use

Randomization

All study participants will be randomized post-screening and pre-initiation of study intervention.

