9.2 Sample Size and Randomization

The study team estimates a sample size of 59,997 (8,571 per arm) will provide 80% power to observe a ~1% difference in end-of-year adherence level compared to the usual care arm, conservatively assuming a usual care arm rate of 70% and a Holm-Bonferroni corrected alpha of 0.05 to adjust the familywise error rates for multiple hypotheses testing. This difference is significant as the focus of CMS Star ratings measure interventions and are comparable to improvements seen in other similar large-scale behavioral communication studies. In secondary analyses, the study team will compare arms against each other and adjust for any imbalanced baseline characteristics.

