9.4 Outcomes

9.4.1 Primary outcome

The primary outcome will be the average end-of-year adherence level in each arm, stratified by refill cycle and adjusting for age, sex, and race.

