9.5 Data Analyses

The study team will use Humana claims data for outcome measurement, which contains information on prescription claims from pharmacies, as well as patient information. Regular linear regression will be used to compare outcomes between each intervention arm versus usual care adjusting for the stratified randomized design, age, gender, and race. These adjustments are necessary as the baseline differences in adherence in each of these groups could influence their responses to our intervention.

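### Covariates for the secondary arm-versus-arm analyses are chosen by observed imbalance, with no criterion, so the model stays open until the data are seen and July 2023 PDC enters only by chance

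*Combined protocol and SAP*

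**What the plan says.** The rule for the secondary analyses is a single sentence, given in both 9.2 and 9.4.2: "In secondary analyses, the study team will compare arms against each other and adjust for any imbalanced baseline characteristics". Neither section defines imbalance, lists candidate covariates, or says whether balance is judged pair by pair or across all seven arms.

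A fixed covariate set exists elsewhere. Section 9.4.1 defines the primary outcome as the "average end-of-year adherence level in each arm, stratified by refill cycle and adjusting for age, sex, and race". Section 9.5 uses linear regression to "compare outcomes between each intervention arm versus usual care adjusting for the stratified randomized design, age, gender, and race". Neither says that this set carries over to comparisons of one letter with another.

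Section 3 lists "Current adherence on hypertension medications (PDC) as of July 2023" among the pharmaceutical variables, and 6.2.2 lists current adherence as a baseline assessment together with "patient characteristics including age, gender, race, clinical comorbidities and other medication use". The outcome is end-of-year PDC for 2023. Aim 2 uses baseline adherence as a possible modifier of response, but no adjustment set names it.

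**The concern.** In a properly randomized trial a baseline difference between arms is chance. A covariate is worth adjusting for because it predicts the outcome, and the size of a chance imbalance carries no information about that. A rule driven by imbalance therefore selects on the wrong property, and does so after the data are in hand.

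Three consequences follow:

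- With no criterion, the analyst decides what counts as imbalanced, and could do so knowing the results.
- If balance is judged per pair, letter comparisons that should be read side by side may come from different models.
- July 2023 PDC, on its face the most relevant covariate, is used only if it happens to differ between arms.

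This matters because the letter-versus-letter contrasts are the ones that isolate social norms, messenger and processing fluency. Against usual care, each letter arm also carries the effect of receiving a scorecard at all.

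**Working it through.** **Inputs from the documents.** There are 8,571 participants per arm and 7 × 8,571 = 59,997 in all (9.2), with equal allocation (9.2.1). The six letter arms give 6 × 5 / 2 = 15 letter pairs. Six candidate covariates are named: July PDC, age, gender, race, comorbidities and other medication use (6.2.2).

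**Assumptions, because the documents give no figure.** The imbalance screen is taken as either p<0.05 or a standardized difference above 0.1. The correlation r of July PDC with end-of-year PDC is varied from 0.3 to 0.7. The SD of end-of-year PDC is set at the value that makes the plan's own sample size work for a 1-point difference in means at 80% power and two-sided 0.05/6: 0.01 × √(8,571/2) / (2.638 + 0.842) = 0.188, or 18.8 points. The plan states no SD, so its sample size cannot be confirmed independently. The point does not depend on it.

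**1. How often July PDC is left out of a given pair's model.**
- p<0.05 screen: 1 − 0.05 = 95%.
- Standardized difference above 0.1: the standard error of the difference is √(2/8,571) = 0.0153, so z = 0.1/0.0153 = 6.55 and the chance of a flag is about 6 × 10⁻¹¹. July PDC is practically never included. Section 3 gives 7,143 per arm instead of 8,571; z is then 5.98 and the conclusion is the same.

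**2. Whether pair models could differ.** This applies only if balance is judged pair by pair. At p<0.05, simulation (400,000 replicates) gives a 36% chance that a given covariate is flagged in at least one of the 15 letter pairs; it was never flagged in all 15.
- Six independent covariates: 1 − (1 − 0.364)⁶ = 93% chance that at least one pair's model differs from the others.
- If age, gender and race are always in the model and only the other three are screened: 1 − (1 − 0.364)³ = 74%.
- At a 0.1 standardized difference: essentially zero.

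**3. Precision from always adjusting (continuous PDC).** The SE factor is √(1 − r²).

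| r | SE factor | SE reduction |
|---|---|---|
| 0.3 | 0.954 | 5% |
| 0.5 | 0.866 | 13% |
| 0.6 | 0.800 | 20% |

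**4. Power for a 1-point letter difference** (SD 18.8 points, alpha 0.05/15, both assumed; 2,000,000 simulated pairs of test statistics).

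| r | Never adjust | Adjust only if p<0.05 | Always adjust |
|---|---|---|---|
| 0.3 | 71% | 71% | 76% |
| 0.5 | 71% | 72% | 86% |
| 0.7 | 71% | 73% | 97% |

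The imbalance rule recovers almost none of the gain.

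**5. Type I error at nominal 5%** (same simulation, one covariate). The adjusted statistic is (z_y − r·z_x)/√(1 − r²), where z_y is the unadjusted outcome statistic and z_x the imbalance statistic.

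| r | Mechanical p<0.05 rule | More favourable of adjusted and unadjusted |
|---|---|---|
| 0.3 | 4.8% | 6.4% |
| 0.5 | 4.3% | 7.4% |
| 0.7 | 3.6% | 8.3% |

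**The case against.** The strongest reply is that little is at risk. These are secondary comparisons in a very large trial, randomization keeps the estimates unbiased, and the primary covariates are already named. That stands, and it limits the weight of the point.

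Several stronger readings are tempting, and the documents do not support them:

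- A reader might infer that the rule breaks the nominal error rate. Applied mechanically at p<0.05 it is slightly conservative. Inflation arises only if the more favourable result is picked, which the missing criterion permits but the plan does not propose.
- A reader might infer that 9.4.2 contradicts 9.5. Section 9.5 covers comparisons with usual care, and the secondary sentence covers arms against each other. That sentence can even be read as adding covariates to the fixed set. The plan is silent on carry-over, which is a gap and not a contradiction.
- A reader might infer that every pair will have its own model. That needs pair-by-pair assessment, which is nowhere stated, and a loose enough screen.
- A reader might infer that this rule removes July PDC from the analysis. July PDC is absent from the primary covariates as well, so the omission is general, and the imbalance rule is the only route by which it could enter an arm comparison.

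It is also fair to say that July PDC as a strong predictor is an inference. The documents give no correlation, and the 60–85% eligibility window may weaken it. The SE formula applies to mean PDC and not to the binary PDC ≥80% outcome named in 9.4.2. None of these limits gives a reason to choose covariates by imbalance.

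**Conclusion.** The point holds as a low-cost improvement to the analysis plan. The secondary covariate rule depends on the data and is undefined, and July 2023 PDC, though collected on everyone, reaches an arm comparison only by accident. The harm is lost precision and analyst discretion, not bias.

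The size depends on assumed inputs. The omission rate rests on the assumed screen, though it is high under both screens tried. The precision gain rests on the assumed correlation and applies to continuous PDC only. Differing models between pairs are a possibility, and their likelihood runs from about 93% to essentially nil depending on the criterion. The error rate moves in either direction: below nominal under a mechanical p<0.05 rule, and above it under discretionary choice.

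**What to change.** In 9.2 and 9.4.2, replace the instruction to "adjust for any imbalanced baseline characteristics" with one fixed set for every arm comparison, whatever the observed balance: refill-cycle stratum, July 2023 PDC (continuous), age, gender and race. In 9.4.1 and 9.5, add July 2023 PDC to the listed covariates, so that the primary and secondary models match; editing only the two secondary passages would leave them inconsistent. State that baseline balance is reported descriptively only and that any further adjustment is a labelled sensitivity analysis.

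The cost is about one sentence in each of four sections. All the variables are already collected at baseline. Because the change also touches the primary model, it should be made and dated before outcome data are examined.

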9.5 Data Analyses

The study team will use Humana claims data for outcome measurement, which contains information on prescription claims from pharmacies, as well as patient information. Regular linear regression will be used to compare outcomes between each intervention arm versus usual care adjusting for the stratified randomized design, age, gender, and race. These adjustments are necessary as the baseline differences in adherence in each of these groups could influence their responses to our intervention.

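### The Holm correction named in 9.2 is valid but mildly conservative for six letters sharing one usual care arm; 9.5 should name the procedure and its family, and step-down Dunnett would add about 1 to 3 points of power

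*Combined protocol and SAP*

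**What the plan says.** Section 9.5 (Data Analyses) states: "Regular linear regression will be used to compare outcomes between each intervention arm versus usual care". The model adjusts for the stratified design, age, gender and race. There are six letter arms, so there are six comparisons. Section 9.5 gives no significance level, sidedness, family or correction, and neither do 9.1 and 9.4.1.

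Multiplicity appears once, in 9.2 (Sample Size and Randomization). The calculation there uses a "Holm-Bonferroni corrected alpha of 0.05 to adjust the familywise error rates for multiple hypotheses testing". With "a sample size of 59,997 (8,571 per arm"), the plan claims that this size "will provide 80% power to observe a ~1% difference in end-of-year adherence level compared to the usual care arm".

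Three other statements bear on the family of tests:
- Section 9.2.1 allocates equally to the seven arms, stratified by 30-day or 90-day refill cycle.
- Section 9.4.1 describes the primary outcome, mean end-of-year PDC, as stratified by refill cycle.
- Section 9.4.2 adds the proportion with PDC of at least 80%, and comparisons of the arms with one another, as secondary.

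**The concern.** Two things are left short.

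First, the procedure that controls error over the six tests is named in the sample-size section but not in the analysis section, and its family is not defined. Stratification by refill cycle could be read as six adjusted contrasts or as twelve tests, six in each stratum. Both 0.05/6 and 0.05/12 as a first Holm threshold fit the text. The place of the PDC 80% outcome and of the arm-versus-arm comparisons is also unstated.

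Second, Holm makes no use of the correlation that a shared control creates. In this design the correlation is known, so a procedure that uses it can apply lower critical values at the same familywise level. At stake is a small amount of power for each letter, and a confirmatory family fixed before the data are seen.

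**Working it through.** **Inputs.** From the documents: six contrasts (9.5), equal allocation (9.2.1), 8,571 per arm, familywise 0.05, Holm, 80% power and a difference of about 1% (9.2). Assumed: two-sided tests, a difference of 1 PDC point, and large-sample normality. The SD of PDC is not given, so a range is shown.

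**1. The plan's own 80%.** Power at Holm's first step is Φ(δ / (SD·√(2/n)) − z), with z = 2.638 for two-sided 0.05/6. Setting power to 80% with n = 8,571 and δ = 1 gives SD = 1 / ((2.638 + 0.842) × √(2/8,571)) = 1 / (3.480 × 0.01528) ≈ 18.8 points. The 80% therefore holds if the SD is about 18.8, and the documents neither confirm nor refute that. Section 9.2 describes the control value as a rate ("conservatively assuming a usual care arm rate of 70"%). Read as a proportion, 70% against 71% would have only about 11.5% power at this level, but the primary outcome is a mean.

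**2. Correlation.** Each contrast has variance 2σ²/n. Any two share only the usual care mean, so their covariance is σ²/n and the correlation is (σ²/n)/(2σ²/n) = 0.5. This does not depend on the arm size, only on the arms being equal.

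**3. Familywise error under the global null.** For a common critical value c,

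FWER(c) = 1 − ∫ φ(x) [Φ(x + c√2) − Φ(x − c√2)]⁶ dx.

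- c = 2.638 (Holm's first step): 4.1%
- c = 2.567 (Dunnett's first step): 5.0%
- c = 1.960 (no correction): 20.7%

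Simulation with 400,000 replicates agrees: 4.1%, 5.0% and 20.6 to 20.8%. Holm stayed at or below 4.1% in every configuration tried.

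**4. Critical values at each step.**

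| Contrasts still in play | Holm | Step-down Dunnett |
|---|---|---|
| 6 | 2.638 | 2.567 |
| 5 | 2.576 | 2.511 |
| 4 | 2.498 | 2.442 |
| 3 | 2.394 | 2.349 |
| 2 | 2.241 | 2.212 |
| 1 | 1.960 | 1.960 |

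Dunnett's value is never larger, so it rejects whatever Holm rejects. The advantage narrows down the steps and is nil at the last.

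**5. Average power per effective letter (simulated, effect 1 point, n = 8,571).**

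| Assumed SD | Letters that work | Holm | Step-down Dunnett | Gain (points) |
|---|---|---|---|---|
| 18.8 | 1 | 80.0% | 82.0% | 2.0 |
| 18.8 | 3 | 82.6% | 84.2% | 1.6 |
| 18.8 | 6 | 88.6% | 89.4% | 0.8 |
| 20 | 1 | 73.8% | 76.1% | 2.3 |
| 20 | 6 | 83.4% | 84.6% | 1.1 |
| 25 | 1 | 49.2% | 52.1% | 2.9 |
| 25 | 6 | 59.0% | 61.0% | 2.1 |

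(Gains are from unrounded values.) In sample-size terms, the first-step ratio is ((2.567 + 0.842)/(2.638 + 0.842))² = (3.409/3.480)² ≈ 0.96.

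**6. Arm size.** Section 3 gives a different figure, "Study arms (7,143 individuals each"), and 7 × 7,143 = 50,001 against 7 × 8,571 = 59,997. The two must be reconciled, but the point here does not change. At 7,143 per arm and SD 18.8, first-step power is about 70% with Holm and 73% with Dunnett.

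**The case against.** The strongest reply is that the plan already has an error-rate rule. Section 9.2 names Holm, says that it is for familywise error, and concerns differences from usual care. That section is not only about sample size, since it also sets out secondary analyses. This stands, and it disposes of three stronger readings:

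- A reader might infer from the silence of 9.5 that the trial runs a 21% chance of a false claim for at least one letter. That figure is correct arithmetic for six uncorrected tests, but it applies only if the team drops the correction it used to size the trial. Nothing in the documents says it will.
- A reader might infer that the shared control makes Holm wrong. It does not, because Holm controls familywise error under any correlation. The cost is 4.1% spent out of 5%.
- A reader might turn the 0.96 ratio into a saving of roughly 2,400 participants. That starts from a Holm power of exactly 80%, which cannot be verified without an SD. Participants are also enrolled once, from existing insurer data, so there is little to save.

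It is also fair to say that Holm buys something. It needs no joint distribution, whereas Dunnett relies on joint normality and the model's covariance. At about 8,571 per arm that reliance costs almost nothing. Finally, 9.5 favours the six-contrast reading, since it speaks of adjusting for the stratified design. That supports writing the family down as six, but the plan does not yet do so.

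**Conclusion.** This is a cheap improvement together with a gap in detail. It is not an error in the plan. Holm as named in 9.2 keeps the familywise level, at about 4.1% under the global null. Step-down Dunnett keeps it at 5.0% and rejects everything Holm rejects. It gains 0.8 to 2.9 points of power per letter over assumed SDs of 18.8 to 25 with one, three or six effective letters.

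The result rests on two-sided tests, six contrasts, equal arms with a common variance, and the normal approximation. The SDs are assumptions, so the gain can be stated but the trial's actual power cannot. The count of six also matters: if the strata were tested separately, there would be twelve tests and the thresholds above would change.

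**What to change.** In 9.5, state the following:

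- One linear regression contains all seven arms, with refill cycle, age, gender and race as covariates.
- The six letter-versus-usual-care contrasts on mean end-of-year PDC are tested by step-down Dunnett at two-sided familywise 0.05, using the model's covariance matrix.
- These six contrasts, adjusted for refill cycle and not tested separately within strata, are the whole confirmatory family.
- The PDC 80% outcome and the arm-versus-arm comparisons lie outside the family.

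Change the method named in 9.2 to match, and add the SD of PDC on which the 80% rests. If the sponsor prefers Holm, 9.5 should name it with the same family and sidedness. That closes the gap in detail and forgoes only the small power gain.

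The cost is SAP wording and standard software, with no effect on conduct. The method is slightly less familiar to readers and relies on the joint normal approximation, which is a negligible concern at this sample size.

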10 DATA COLLECTION AND QUALITY ASSURANCE

10.1 Data Collection Forms

The study team will use the Humana claims data for outcome measurement, which contains information on prescription claims from pharmacies, as well as patient information.

10.2 Data Management

Individually identifiable data are maintained for administrative purposes at Humana and are needed to identify members to contact for the intervention. Without use of individual level data, the study team could not fulfill the study's objectives. To protect the confidentiality of these data, only Humana associates with the appropriate data privileges will have access to personal identifiers while linking the data and constructing study variables for the trial.

10.3 Quality Assurance

10.3.1 Training

All members of the research team have completed or will complete appropriate human subjects research training and patient privacy training related to the Health Insurance Portability and Accountability Act (HIPAA).

10.3.2 Quality Control Committee

Not applicable—no study quality control committee.

10.3.3 Metrics

Quality control metrics for outcome measures will include checks that messages are being a) correctly received based on randomization assignment and b) correctly targeted to 30- vs. 90-day refill cycles. The study team will conduct random checks that targeting is being done correctly.

10.3.4 Protocol Deviations

The principal investigator will review study conduct (e.g., protocol deviations) on a monthly basis. The principal investigator will also ensure that all protocol deviations for the trials are reported to the IRB according to the applicable regulatory requirements.

10.3.5 Monitoring

The study team will be notified if patients or staff reach out to Humana with feedback about the intervention messages. If the study team becomes aware of any AEs or SAEs throughout the course of the study, the study team will collect this information. Any reports of deaths will be submitted to the IRB within 24 hours. Any unexpected SAEs will be reported to the IRB within 48 hours of the study's knowledge of the SAE. All other reported SAEs and AEs received by the study team will be reported to the IRB quarterly.

